# 3 Abbreviations

AE/AR	Adverse event/Adverse Reaction
AED	Anti-Epileptic Drug
CA	Competent Authority
CCTU	Cambridge Clinical Trials Unit
CRF	Case Report Form
CTC	Clinical Trial Co-ordinator (Central)
CTIMP	Clinical Trial of Investigational Medicinal Product
DMC	Data Monitoring Committee
DSUR	Development Safety Update Report
EQ-5D-5L	Health related quality of life assessment (based on 5 dimensions each of which have 5 levels)
GP	General Practitioner
GCP	Good Clinical Practice
GDPR	General Data Protection Regulations
GOS	Glasgow Outcome Scale
HES	Hospital Episode Statistics
HTA	Health Technology Assessment
ICF	Informed Consent Form
IHP	Independent Healthcare Professional
IMP	Investigational Medicinal Product
MHRA	Medicines and Healthcare products Regulatory Agency
NIMP	Non Investigational Medicinal Product
NSI	Neurobehavioural Symptom Inventory
NSU	Neurosurgical unit
PIS	Participant Information Sheet
PSS	Personal Social Services
PTS	Post-Traumatic Seizures
R&D	Research and Development
RA	Regulatory Agency
REC	Research Ethics Committee
SAE/SAR	Serious Adverse Event/Serious Adverse Reaction
SUSAR	Suspected Unexpected Serious Adverse Reaction
TBI	Traumatic brain injury
TMG	Trial Management Group
TSC	Trial Steering Committee

[figure not shown]
# 4 Trial Synopsis

Title of clinical trial	Pharmacological management of seizures post traumatic brain injury
Sponsor name	Cambridge University Hospitals NHS Foundation Trust and the University of Cambridge
EudraCT number	2020-000282-16
Medical condition or disease under investigation	Seizures post-traumatic brain injury
Purpose of clinical trial	
 
To assess 
 
Anti-epileptic drug (AED) prophylaxis following traumatic brain injury (TBI) (MAST-PROPHYLAXIS)
 
Duration of AED treatment following post- traumatic seizure(s) (PTS) (MAST- DURATION)
 

	This will be assessed by conducting 2 parallel but independent trials. Eligibility to enter either trial will be dependent on whether an early seizure has occurred.
Primary objective	MAST_PROPHYLAXIS:To determine the comparative clinicaleffectiveness (absolute difference in the rate ofPTS within the first 2 weeks post-TBI) of a 7-daycourse of phenytoin or levetiracetam, used asseizure prophylaxis, versus no AED for TBIpatientsMAST-DURATION:To determine the comparative clinicaleffectiveness (absolute difference in the rate oflate PTS within 24 months post-TBI) of a longercourse of phenytoin or levetiracetam (at least 6months) versus a shorter course (up to 3 months)for TBI patients with early seizures
Secondary objective (s)	
 
MAST-PROPHYLAXIS:
 
1. Compare the rate of PTS within 24 months post-TBI
 
2. Compare outcomes (extended Glasgow Outcome Scale), cognitive function (Neurobehavioural Symptom Inventory), quality of life (EQ-5D-5L), and adverse events (Liverpool Adverse Events Profile) at 6, 12, 18 and 24 months, between the three arms.
 
3. Undertake a detailed economic evaluation.
 
4. To compare the frequency of PTS between the three arms.
 
5. Mortality at 6, 12, 18 and 24 months.
 
6. Adverse events of special interest during treatment.
 

	MAST-DURATION: 1. Compare outcomes (extended Glasgow Outcome Scale), cognitive function

Trial Design	
 
(Neurobehavioural Symptom Inventory), quality of life (EQ-5D-5L), and adverse events (Liverpool Adverse Events Profile) at 6, 12, 18 and 24 months, between the two arms.
 
2. Undertake a detailed economic evaluation.
 
3. To compare the frequency of PTS between the two arms.
 
4. Mortality at 6, 12, 18 and 24 months.
 
5. Adverse events of special interest during treatment.
 
 MAST-PROPHYLAXIS : Phase 3, randomised multi-centre, pragmatic, parallel group trial.
	multicentre, pragmatic, parallel group trial
	multicentre, pragmatic, paraller group that
	Both studies will start with an internal pilot study.
Trial Outcome Measures	Primary outcome measure:
Thai Outcome Measures	
 
MAST-PROPHYLAXIS: Occurrence of PTS within 2 weeks after TBI.
 
MAST-DURATION: Occurrence of late PTS within 24 months after TBI.
 
Secondary outcome measures:
 

	-
	PTS up to 2 years (MAST-PROPHYLAXIS
	only)
	Extended Glasgow Outcome Scale,
	Neurobehavioural Symptom Inventory,
	quality of life (EQ-5D-5L), and Liverpool Adverse Events Profile at 6, 12, 18 and 24
	months.
	Economic evaluation
	
 
Frequency of PTS
 

	
 
Mortality at 6, 12, 18 and 24 months.
 

	
 
Adverse events of special interest during
 

	treatment.
Sample Size	Recruitment of:
Sample Size	MAST-PROPHYLAXIS: 1221 patients in total
	(130 in an internal pilot)
	MAST-DURATION: 428 patients in total (50 in an
	internal pilot)
Summary of eligibility criteria	MAST-PROPHYLAXIS
	Inclusion Criteria:
	
 
Patients aged ≥10 years, with TBI
 

	managed in an NSU without an acute
	symptomatic seizure
	Patient or Legal Representative is willing
	and able to provide informed consent or in
	the absence of a legal representative, an
	Independent Healthcare Professional
	provides authorisation for patient enrolment
	Exclusion Criteria
	Post-traumatic seizures

	
 
Un-survivable injury
 
Previous history of epilepsy
 
Patients who are on an AED pre-TBI
 
Pregnancy or breastfeeding
 
Any hypersensitivity to study drug (or hydantoins or pyrrolidone derivatives) or any of its excipients
 
Time interval from the time of admission to NSU to randomisation exceeds 48 hours
 

	MAST-DURAHON
	
 
Inclusion Criteria:
 
Patients aged ≥10 years with TBI managed in an NSU who have started on phenytoin or levetiracetam due to an acute symptomatic seizure during acute hospitalisation
 
Patient or Legal Representative is willing and able to provide informed consent or in the absence of a legal representative, an Independent Healthcare Professional provides authorisation for patient enrolment
 

	
 
Exclusion Criteria:
 
Un-survivable injury
 
Previous history of epilepsy
 
Patients who are on an AED pre-TBI
 
Patient who has been clinically prescribed an AED to treat PTS (other than phenytoin or levetiracetam) since current admission
 
Any hypersensitivity to study drug selected or any of its excipients
 

Investigational medicinal product	Phenytoin as prescribed clinically
and dosage	Levetiracetam as prescribed clinically In MAST-DURATION the choice of AED (phenytoin or levetiracetam) will be at the discretion of local clinical teams.
Route(s) of administration	Oral, nasogastric tube, IV
Maximum duration of treatment of a participant	MAST-PROPHYLAXIS: 7 days MAST-DURATION: Up to 24 months dependent on clinical need
Procedures: Screening & enrolment	Review of clinical situation (TBI patients) will be undertaken by a member of the clinical team. Informed consent will be obtained from the patient, patient's representative (if the patient lacks capacity) or by agreement with an independent clinician.

Procedures: Baseline	
 
Inclusion/exclusion criteria review
 
Informed consent process followed and consent or authorisation for enrolment obtained.
 
Standard of Care
 
Patient medical history (including comorbidities and relevant medications) and patient demography
 
Neurological status
 
Imaging modality and date of examination
 
Presence of PTS during the treatment period / after the prophylaxis
 
				
Procedures: Treatment period	
 
Standard clinical monitoring to discharge
 
Follow up at 14 days (PROPHYLAXIS)
 
Follow up at 6 months (+/- 8 weeks)
 
Follow up at 12 months (+/- 8 weeks)
 
Follow up at 18 months (+/- 8 weeks)
 
Follow up at 24 months (+/- 8 weeks)
 
				
Procedures: End of trial	The date of the last patient's final assessment/loss to follow-up.				
Procedures for safety monitoring during trial	All results will be forwarded to the Data Monitoring Committee (DMC) who will address safety issues. Any significant adverse results will be reported to the DMC via the Trial Coordinating Centre (CCTU). Onward reporting to the TSC and Sponsor.				
Criteria for withdrawal of participants	
 
SUSAR
 
Withdrawal from treatment - participants may voluntarily withdraw from treatment for any reason at any time, but continue to provide follow-up data
 
Withdrawal from trial - participants may voluntarily withdraw from treatment for any reason at any time, and also withdraw from data collection
 
Patients will be withdrawn at any time if the investigator concludes that it would be in the patient's best interest for any reason
 
				
Randomisation	Randomisation in MAST-PROPHYLAXIS will occur within 48 hours from admission to NSU. Randomisation in MAST-DURATION can occur at any time point during acute hospitalisation in the NSU as long as the patient has been started on Phenytoin or Levetiracetam due to post-traumatic seizures.				

# 6 Introduction

# 6.1 Background

Traumatic brain injury (TBI) is an alteration in brain function or other evidence of brain pathology, caused by an external force .It is a major public health problem that can result in physical, cognitive, functional and psychosocial disability . The majority of patients who have a TBI do not need to stay in hospital. However, approximately 9,000 patients require admission to a specialist hospital each year in the UK, as their injury is more serious . Post-traumatic seizures (PTS) are well recognised following TBI . They are classified as acute symptomatic or provoked (within 7 days post-TBI) or late (after 7 days). Seizures during acute hospitalisation can lead to significant derangement of brain physiology and can even lead to brain herniation and death. Additionally, PTS during acute hospitalisation have been shown to be an independent risk factor for PTS within 12 and 24 months following TBI . Late PTS within 24 months can have a negative impact on quality of life, return to work, return to driving, and can even result in death.

Current international guidelines for traumatic brain injury (TBI)  recommend the use of phenytoin for the prevention of early PTS when the benefits are thought to outweigh the risks, however the inadequacy of current evidence underpins this guidance. In practice alternative antiepileptic drugs (AEDs) such as levetiracetam and valproate are being used clinically as they are believed to have a more favourable risk profile. This is despite there being insufficient evidence to support their efficacy, or indeed that of phenytoin. In fact at the moment it remains unclear which AED treatment is more appropriate in patients with PTS and for how long patients should be treated. It is also unclear if prophylaxis for PTS following TBI is clinically effective, which patients might benefit from this treatment and for how long the drug should be given. The only evidence currently available dates back to 1990 when Temkin et al. showed a reduced incidence of rate of early seizures from 14.2% to 3.6% after administration of phenytoin .

Acute symptomatic seizures are potentially harmful. Recurrent PTS after TBI can negatively impact on quality of life, return to work/driving, and can even lead to death. AEDs are the mainstay of treatment for patients with PTS but are associated with side effects that, if serious, can negatively impact on quality of life, cognition, and general health . Patients with acute symptomatic seizures are typically started on an AED in order to prevent seizure recurrence. The optimal duration of treatment remains unclear. MAST-DURATION will compare a long course of AED (at least 6 months) vs a shorter course (up to 3 months). The duration of AED treatment in the two arms was determined on the basis of our recent ÚK-wide survey  and consensus among the multidisciplinary group of co-applicants. Additionally, we decided to include only patients who have been started on phenytoin or levetiracetam by the clinical teams on the basis of i) feedback by the HTA funding committee during assessment of the stage 1 application and ii) the fact that these two AEDs are used by over 90% of clinicians who completed our survey. Our survey  was completed by 117 respondents, predominantly neurosurgeons (76%) from 30 (of 32) trauma-receiving hospitals in the UK and Ireland. The main results were: 53% of respondents do not routinely use seizure prophylaxis, but 38% of those that do, prescribe prophylaxis for one week. 60% feel there is uncertainty regarding the use of seizure prophylaxis, and 71% would participate in further research to address this question. 62% of respondents use levetiracetam for treatment of seizures during the acute phase, and 42% continued for a total of 3 months. Overall, 90% were uncertain about the duration of treatment for seizures, and 78% would participate in further research to address this question. Our survey also showed that almost half of the respondents use a short AED course as seizure prophylaxis, even though this practice is only supported by low-quality evidence . MAST-PROPHYLAXIS will compare a 7-day course of AED (either levetiracetam or phenytoin) versus no AED.

Phenytoin is an AED that was introduced in the 1930's and now is still widely used in clinical

practice. Its main mechanism of action is by blocking voltage-dependent sodium channels  and it can be administered both orally or intravenously. Due to its unpredicatable pharmacokinetics, drug interactions and competition for protein binding, in acute situations, such as seizures following TBI, blood plasma levels should be monitored initially until stability and then a continued dose maintained. Plasma levels are not routinely checked after this unless further seizures occur or if required for other clinical reasons, then doses would be adjusted as required. Side effects include thrombophlebitis, extravasation injury and arrhythmia when given intravenously and include gingival hypertrophy, body hair increase, rash and folic acid depletion in oral or intravenous preparations

Levetiracetam has efficacy against focal onset seizures and its main mechanism of action is thought to be via binding to the SV2 synaptic vesicle . Due to its small potential for pharmacokinetic interactions with other drugs, the fact it does not require a titration period  or routine monitoring of plasma levels it has become a very common AED in clinical practice. In the acute setting a loading dose can be administered. Side effects include drowsiness, mood alterations and some longer term behavioral disturbances . Side effects and adherence will be monitored and recorded during the follow up period in both studies. A recommended dosing strategy will be outlined in the protocol to include loading doses and plasma monitoring as required.

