#### 8.6.2 Secondary outcome measures (both trials)

- Occurrence and time to PTS within 24 months post-TBI (MAST-PROPHYLAXIS ONLY)
- Extended Glasgow Outcome Scale, Neurobehavioral Symptom Inventory, quality of life (EQ-5D-5L), and Liverpool Adverse Events Profile at 6, 12, 18 and 24 months.
- Economic evaluation
- Frequency of PTS
- Mortality at 6, 12, 18 and 24 months.
- Adverse events of special interest during treatment.

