#### 10.1.2.6 Administration

Phenytoin can be administered orally, intravenously or via a nasogastric tube.

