# 12.1 Definitions

## 12.1.1 Adverse event (AE)

Any untoward medical occurrence in a participant or clinical trial participant administered a medicinal product and which does not necessarily have a causal relationship with this treatment.

An adverse event can therefore be any unfavourable and unintended sign (including an abnormal laboratory finding), symptom, or disease temporally associated with the use of an investigational medicinal product, whether or not considered related to the investigational medicinal product.

Please note: Recording of adverse events must start from the point of Informed Consent regardless of whether a participant has yet received a medicinal product.

However due to the pathology of traumatic brain injury, where the patients will be regularly monitored in the intensive care environment or on the neurosurgical wards, it is not practicable to record all adverse events. Therefore only adverse events of special interest (AESIs) will be recorded and **reportable** serious adverse events (SAEs) will be reported in accordance with this protocol. (Please see Section 12.1.4 for details of SAEs that are exempt from expedited reporting.)

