#### Phenytoin arm

- Cardiovascular: Cardiac arrhythmia, circulatory shock;
- Central nervous system: phenytoin toxicity (nystagmus +/- unsteady gait +/- slurred speech +/- confusion). Drowsiness, suicidal ideation/tendencies;
- Dermatologic: Bullous dermatitis, skin rash;
- Gastrointestinal: Gingival hyperplasia;
- Genitourinary: Peyronie's disease;
- Hematologic: Macrocytosis, megaloblastic anaemia;
- Hepatic: Dupuytren's contracture, hepatitis ;
- Injection site reaction: Purple glove syndrome: oedema, discolouration and pain distal to injection site.

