## 12.3 Expected Adverse Events/Serious Adverse Events (AE/SAE)

#### Expected SAEs exempt from expedited reporting

Due to the nature of traumatic brain injury, affected individuals can often develop surgical and medical complications. Expected systemic or surgical complications associated with TBI will not be reported as SAEs However, all SAEs (both reportable or non-reportable) will be captured on the study CRF (Case Report Form) or SAE recording log in the Investigator Site File, so that all serious adverse event data is captured.

In addition, any of the following systemic SAEs are also exempt from expedited reporting:

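### Two intravenous phenytoin side effects named in the protocol's background are not named on the AESI list, so non-serious cases in the 7-day PROPHYLAXIS course would largely go uncounted

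*Protocol*

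**What the plan says.** Section 6.1 (Background) lists the side effects of phenytoin by route: "Side effects include thrombophlebitis, extravasation injury and arrhythmia when given intravenously". For oral or intravenous use it adds gum overgrowth, increased body hair, rash and folic acid depletion. For levetiracetam it names drowsiness, mood changes and longer-term behavioural disturbance. The same section states that side effects will be monitored and recorded during follow-up in both studies.

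The intravenous route is open to trial patients. Section 10.1.2.6 reads: "Phenytoin can be administered orally, intravenously or via a nasogastric tube".

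Section 12.1.1 explains that recording every adverse event is impracticable in intensive care and on neurosurgical wards, and concludes: "Therefore only adverse events of special interest (AESIs) will be recorded", alongside reportable serious adverse events. The phenytoin list that follows includes "Cardiovascular: Cardiac arrhythmia, circulatory shock" and one local item: "Injection site reaction: Purple glove syndrome: oedema, discolouration and pain distal to injection site". Thrombophlebitis and extravasation injury are not named on either drug's list.

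Section 8.6.2 makes "Adverse events of special interest during treatment" a secondary outcome of both trials. It also lists "quality of life (EQ-5D-5L), and Liverpool Adverse Events Profile at 6, 12, 18 and 24 months". Section 12.3 states that "all SAEs (both reportable or non-reportable) will be captured on the study CRF" or on a log in the site file.

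**The concern.** Section 8.5.1 makes comparison of adverse events between the three PROPHYLAXIS arms a secondary objective. Section 6.1 says that other drugs are used in place of phenytoin because they are thought to carry a better risk profile, so tolerability is part of what the trial should inform. The AESI outcome can count only what the form asks for. The protocol itself attributes three side effects to intravenous phenytoin, and the list names one of them. The other two are local infusion harms. In PROPHYLAXIS they would arise during the 7-day in-hospital course, where the AESI assessment is the scheduled harm assessment. If non-serious cases are not recorded then, they may not be reliably recoverable later.

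**Working it through.** The check is a comparison of text. The protocol states no figure on this point that could be reproduced.

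**1. Side effects in section 6.1 against the AESI lists in section 12.1.1**

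| Side effect in section 6.1 | Drug | On that drug's AESI list? |
|---|---|---|
| Arrhythmia (intravenous) | Phenytoin | Yes, by name |
| Extravasation injury (intravenous) | Phenytoin | Not named; partial overlap with the purple glove item |
| Thrombophlebitis (intravenous) | Phenytoin | Not named, not clearly covered |
| Gum overgrowth | Phenytoin | Yes, as gingival hyperplasia |
| Rash | Phenytoin | Yes |
| Folic acid depletion | Phenytoin | Indirectly, through macrocytosis and megaloblastic anaemia |
| Increased body hair | Phenytoin | No |
| Mood and behavioural change | Levetiracetam | Yes, through the behavioural items |
| Drowsiness | Levetiracetam | No; it is on the phenytoin list |

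The purple glove item is defined by signs distal to the injection site. An extravasation injury with distal swelling and discolouration could be entered under it. One confined to the site, or an inflamed vein, does not fit the wording.

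**2. Whether another route captures non-serious cases in PROPHYLAXIS**

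- *Serious events.* Section 12.3 captures all of them, and section 12.1.4 counts important medical events as serious. Serious local injury is covered; non-serious injury is not.
- *Liverpool Adverse Events Profile.* Its first time point is 6 months (sections 8.6.2 and 11.6). It is unlikely to pick up a local reaction from a 7-day course.
- *General recording instruction.* Section 12.4.4 sends adverse events and reactions to the notes and to the CRF or a log. This sits uneasily with the restriction in section 12.1.1. Section 12 also tells principal investigators that they need not report such events centrally unless they are serious reactions. Even where followed, section 12.4.4 places the event in no compared outcome.
- *AESI form.* Section 11.6 schedules it at Day 1 and Day 7 in PROPHYLAXIS. It is the only scheduled harm assessment in the treatment window.

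**3. Size**

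Allocation is 1:1:1 with 1221 patients, so 1221 / 3 = 407 are allocated to phenytoin. The number of uncounted cases is

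407 × (share given the drug intravenously) × (rate of non-serious thrombophlebitis or extravasation injury) × (1 − fraction entered under the purple glove item).

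None of the last three terms is in the protocol. Purely as an illustration, assume that every patient is treated intravenously, that nothing is entered under the purple glove item, and that 5% to 20% have such an event. Then 407 × 0.05 ≈ 20 and 407 × 0.20 ≈ 81. Any lower intravenous share, or any capture under the existing item, reduces these counts.

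**The case against.** The best defence is that an AESI list is a selection by design. Section 12.1.1 gives the reason for selecting, sections 10.1 and 12 set out a risk-adapted approach for well-known drugs, and nothing obliges the list to reproduce the background text. Serious cases are captured in any event. This stands, and it is why the point is minor. It does not explain why two of the three harms that the protocol singles out for the intravenous route were left off a list that includes items such as Peyronie's disease and Dupuytren's contracture.

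Four stronger readings are tempting, and the protocol does not support them.

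- *Phenytoin's harm as a whole is understated, so the comparison with levetiracetam favours phenytoin.* This is not shown. The phenytoin list spans eight categories and the levetiracetam list one. Drowsiness, which section 6.1 attributes to levetiracetam, is sought only on the phenytoin list. The net direction against levetiracetam is unclear and could be the reverse.
- *AESIs are the only non-serious events compared.* They are not: the Liverpool profile is also compared. It simply starts too late for the PROPHYLAXIS course, and in DURATION it can fall during treatment.
- *Extravasation injury is wholly uncounted.* The purple glove item overlaps with it in part.
- *Some 20 to 81 patients would be missed.* Those counts rest on an assumed rate applied to every allocated patient whatever the route, although section 10.1.2.6 also allows oral and nasogastric use.

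Nor does the point carry over to DURATION. There the clinician chooses the drug, it is started before randomisation, and the randomised contrast is length of treatment.

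**Conclusion.** The point holds in limited form. The AESI list names neither thrombophlebitis nor extravasation injury, and its injection-site item covers the second in part and the first not at all. With recording restricted as in section 12.1.1, non-serious cases in the 7-day PROPHYLAXIS course would largely be missing from the AESI outcome. For these two local harms the effect is an undercount in the phenytoin arm, most plainly against no AED. No claim is made about overall bias between phenytoin and levetiracetam. The magnitude is unknown for want of an incidence and an intravenous share. The conclusion assumes that sites follow section 12.1.1 rather than the broader instruction in section 12.4.4, and that they read the purple glove item as written. The primary outcome, power and significance level are untouched. Severity is minor.

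**What to change.** Add two fixed yes/no items to the AESI form, one for thrombophlebitis and one for extravasation or other infusion-site injury. Ask them in the same words in all three PROPHYLAXIS arms at the existing Day 7 assessment.

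In the same edit, reconcile the remaining side effects in section 6.1 with the two AESI lists. Drowsiness for levetiracetam and increased body hair for phenytoin are the visible gaps. Each should either be added or be left out for a stated reason.

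The DURATION comparison needs no change.

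The cost is slightly more data entry on an existing form at an existing visit. Cannula-related events unconnected with the trial drug will also be counted in every arm. Asking identically in all arms lets that background be seen and compared.
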